### **8.2.3. Adverse Events Leading to Discontinuation of Study Treatment and Other Significant Adverse Events**

For the IB only (the team will utilise RAPIDO DV for the CSR) a listing of AEs leading to permanent discontinuation of study treatment will be produced. AEs leading to a discontinuation of either GSK3745417 or dostarlimab for the Part 2A and crossover cohorts will be included.

### **8.2.4. Dose Limiting Toxicity**

A summary of dose-limiting toxicities during the determinative period will be provided and will be performed on the DLT evaluable population. See Section 0 for details on which participants and cohorts are included in the DLT evaluable population and what the determinative (DLT evaluable) period is for each treatment cohort. Note that the crossover cohorts do not form part of the DLT evaluable analysis set and so are excluded.

The listing of all AEs will include the Dose-Limiting Toxicity flag (Yes/No) at the AE level and the DLT evaluable flag (Yes/No) at the participant level.

## **8.3. Clinical Laboratory Analyses**

Laboratory tests are listed the protocol Appendix 2, Table 26 and will be based on GSK Core Data Standards. The tests include hematology, chemistry, coagulation, cardiac function, thyroid function, and urinalysis tests.

All laboratory test values (excluding urinalysis) will be categorised as within the normal range, high or low with respect to normal range.

For laboratory tests which are gradable, values will be graded and reported using the CTCAE version 5.0. In some cases, there will be two bi-directional parameters (hyper- and hypo-) created and the tests will be graded by CTCAE version 5.0 in both directions.

For the following laboratory parameters, every participant will be assessed separately for low and/or high values. The following groups indicate whether laboratory severity grades are assessed according to a low value, high value, or separately for both low and high values.

- Low Value: Maximum Severity (Grade 4) for the following laboratory tests: white blood cells (WBC), neutrophils, platelets, and albumin; Normal Range only for the laboratory tests: red blood cells (RBC), haematocrit, total protein and basophils.
- High Value: Maximum Severity (Grade 4) for the following laboratory tests: alanine aminotransferase (ALT), aspartate transferase (AST), total bilirubin, alkaline phosphatase and creatinine; Normal Range only for the laboratory tests: blood urea nitrogen (BUN), and eosinophils.
- Low and High Values: Potassium, sodium, glucose, calcium, haemoglobin, lymphocytes will be assessed for the maximum severity grade for both low and high values. Monocytes will be assessed for the Normal Range only for both low and high values. For these laboratory parameters, every participant will be assessed separately for high and low values (i.e., separate summary on severity grade/normal range will be produced for high glucose (hyperglycemia) and low glucose (hypoglycemia), high potassium (hyperkalemia) and low potassium (hypokalemia), high sodium (hypernatremia) and low sodium (hyponatremia), high calcium (hypercalcemia) and low calcium (hypocalcemia), high hemoglobin (hemoglobin increased) and low hemoglobin (anemia), high lymphocytes (lymphocyte count increased) and low lymphocytes (lymphocyte count decreased) and high monocytes (monocytosis) and low monocytes (monocytopenia).

A listing of all laboratory data for participants with any value outside of normal range will be produced. The listing will include treatment group, site ID, unique subject ID, subject ID, age, sex, race detail, lab test with units, term, planned timepoint, date, study day, period day, value, normal range, change from baseline, normal range flag (Low/Normal Range/High), and grade. Crossover cohorts will be included in the listing.

A listing of urinalysis data for participants with any value of potential clinical importance will be generated. Crossover cohorts will be included in the listing.

### **8.3.1. Analyses of Liver Function Tests**

A summary of hepatobiliary laboratory abnormalities will be provided. Crossover cohorts will be included.

When a liver stopping or monitoring event has occurred, as defined in the protocol, the Liver Event Reporting form should be completed. A liver stopping event profile will be generated and can be reviewed in RAPIDO DV along with liver restart/re-challenges data. Crossover cohorts will be available to view.

## **8.4. Other Safety Analyses**

### **8.4.1. ECG**

The key ECG measurement taken in this study will be the uncorrected QT interval (msec). The QT correction (QTc) will then either be calculated automatically or it will be calculated manually using the Fridericia formula (QTcF, msec). In the case QTcF is required to be calculated manually, RR interval (msec) will also be recorded on the eCRF. Additionally, an overall interpretation of the ECG reading will be provided (normal, abnormal not clinically significant, abnormal clinically significant, no result or unable to evaluate).

The QTc values based on Fridericia formula will be rounded to an integer and the values will be categorized into the following ranges: Grade 0 (<450), Grade 1 (450-480), Grade 2 (481-500), and Grade 3 ( $\geq 501$ ). Results categorized as Grade 1 and above will be considered of potential clinical importance (PCI). The results will be categorized as ‘No Change or Decrease to <450’, ‘Any Increase  $\geq 450$ ’, ‘Increase to  $\geq 450$  to  $\leq 480$ ’, ‘Increase to  $\geq 481$  to  $\leq 500$ ’ and ‘Increase to  $\geq 501$ ’.

The change from baseline in QTcF values will be categorized into the clinical concern ranges (and flagged as PCI): 31-60 and >60 msec.

ECG data can be viewed using RAPIDO DV - no static displays will be produced. Crossover cohorts will be available to view. For the numeric results recorded in triplicate, all available values will be available to view.

### **8.4.2. Vital Signs**

Vital signs values will be categorized as follows:

- Systolic blood pressure (BP, mmHg): Grade 0 (<120), Grade 1 (120-139), Grade 2 (140-159) and Grade 3 ( $\geq 160$ )
- Diastolic BP (mmHg): Grade 0 (<80), Grade 1 (80-89), Grade 2 (90-99), and Grade 3 ( $\geq 100$ )
- Pulse rate (beats/min): Low (<60), Normal (60-100), and High (>100)
- Temperature in degrees C: ‘Decrease to  $\leq 35$ ’, Normal (36-37), ‘Increase to  $\geq 38$ ’

Vital signs data can be viewed using RAPIDO DV - no static displays will be produced. Crossover cohorts will be available to view.

### **8.4.3. LVEF**

LVEF data can be viewed using RAPIDO DV - no static displays will be produced. Crossover cohorts will be available to view.

#### **8.4.4. Performance Status**

Eastern Cooperative Oncology Group (ECOG) performance status data can be viewed using RAPIDO DV - no static displays will be produced. Data after crossover do not need to be available to view in RAPIDO DV.

#### **8.4.5. COVID-19 Analyses**

Relationship to COVID-19 will be included in the following listings:

- Listing of Reasons for Study Withdrawal
- Listing of Reasons for Study Treatment Discontinuation from GSK3745417
- Listing of Reasons for Study Treatment Discontinuation from Dostarlimab
- Listing of Important Protocol Deviations

COVID-19 infection data can be viewed using RAPIDO DV - no static displays will be produced. Data after crossover do not need to be available to view in RAPIDO DV.

#### **8.4.6. Pregnancies**

While pregnancy itself is not considered to be an AE or SAE, any pregnancy complication or elective termination of a pregnancy for medical reasons will be reported as an AE or SAE.

Pregnancy data can be viewed using RAPIDO DV - no static displays will be produced. Data after crossover do not need to be available to view in RAPIDO DV.

## 9. PHARMACOKINETIC ANALYSES

The PK analyses will be based on the Pharmacokinetic analysis set, unless otherwise specified. While participants will be assigned to the cohort of the actual treatment dose level received at first dosing (that is, in terms of categorisation and ordering in displays), their PK data will be summarized by the actual dose received for each visit.

Note that PK analyses will only be performed on GSK3745417 and not on dostarlimab. PK summary tables will include columns for treatment groups only (a total column within each Part will not be included). Refer to Section 12.5.3 for PK reporting standards. Crossover cohorts will be included in all PK displays where space allows (some figures are restricted to certain visits, so may not include crossover visits).

### 9.1. Drug Concentration Measures

Blood sampling time will be related to the start of dosing.

GSK3745417 plasma serum concentration-time data will be listed by treatment group. The listing will include treatment group, site ID, unique subject ID, subject ID, age, sex, race detail, visit, date, study day, period day, actual dose (mg), planned relative time, actual time, time deviation, actual relative time, lower limit of quantification (LLQ) value for the assay, concentration results and PK analysis exclusion flag. Values below the LLQ are recorded as Not Quantifiable (NQ), see Section 12.5.3.

The PK analysis exclusion flag indicates which samples are excluded from the PK concentration tables and figures and the PK parameter analysis. In general, the following samples will be excluded:

- Where VISITNUM is missing.
- When PCDTC is missing.
- Pre-treatment pre-dose records (e.g. Week 1) with quantifiable results: pre-treatment pre-dose records should have NQ and those records are included in the PK concentration tables and figures.
- Post-treatment pre-dose records (e.g. Week 2+) with higher PK concentration than final record from previous treatment cycle (e.g. Week 1 EOI+24 HR)

The final list of exclusions (that is, samples that will have the PK analysis exclusion flag as “Yes”) will be provided by CPMS.

GSK3745417 plasma concentration-time data will be summarized by treatment and nominal time using descriptive statistics (n, number imputed, mean, 95% confidence interval [CI], standard deviation [StD], median, minimum, and maximum). If more than 30% of values at a time-point are imputed, then standard deviation will not be reported.

Linear and semi-logarithmic individual concentration-time profiles (by treatment and participant) and mean (+StD) and median profiles by GSK3745417 dose will be plotted.

For the table and figures, NQ values will be imputed as per Section 12.5.3.

Urine concentration data will be made available in RAPIDO DV, see Section 1, when available for participants.

### 9.1.1. Lower Limit of Quantification (LLQ) values

Three assays were used for PK analysis in this study, with each assay having its own LLQ. In general, the following assays and LLQs were used:

- Samples analyzed prior to June 2019: assay with LLQ of 0.005 ng/mL.
- Samples analyzed from June 2019 to August 2020: assay with LLQ of 5 ng/mL.
- Samples analyzed after August 2020: assay with LLQ of 0.1 ng/mL.

In general, the time of the analysis determined the assay, and therefore, the same assay may not have been used for all samples from a participant. There may have been exceptions to the general guidance above, and the concentration-time listing will include the LLQ value for the assay used for each measurement.

## 9.2. Derived Pharmacokinetic Parameters

### 9.2.1. Variables

Pharmacokinetic parameters for GSK3745417 administered intravenously in this study will be calculated by standard non-compartmental analysis according to current working practices and using the currently supported version of Phoenix WinNonlin.

All calculations of non-compartmental PK parameters will be based on actual sampling times. For each participant and for each dose, additional pharmacokinetic parameters may be derived as described in [Table 3](#) will be determined from the GSK3745417 plasma serum concentration-time data, as data permit.

**Table 3** **Derived Pharmacokinetic Parameters**

Parameter	Parameter Description
AUC(0-t)	Area under the plasma/serum concentration-time curve from time zero to the time of the last quantifiable concentration (C(t)) will be calculated using the linear trapezoidal rule for each incremental trapezoid and the log trapezoidal rule for each decremental trapezoid.
AUC(0-tau)	Area under the plasma/serum concentration-time curve during the dosing interval using the linear/log trapezoidal rule.
AUC(0-inf)	For single dose. Area under the plasma/serum concentration-time curve from time zero extrapolated to infinity will be calculated as: $AUC(0\text{-}inf) = AUC(0\text{-}t) + C(t) / \lambda_z$
%AUCex	For single dose. The percentage of AUC (0-inf) obtained by extrapolation (%AUCex) will be calculated as: $[\text{AUC}(0\text{-}inf) - \text{AUC}(0\text{-}t)] / \text{AUC}(0\text{-}inf) \times 100$

Parameter	Parameter Description
Cmax	Maximum observed plasma/serum concentration, determined directly from the plasma/serum concentration-time data.
Lambda_z	Terminal phase elimination rate constant. For single dose. The lambda_z lower and upper limits and number of points used to determine lambda_z will also be reported.
tmax	Time to reach Cmax, determined directly from the plasma/serum concentration-time data.
t½	For single dose. Apparent terminal phase half-life will be calculated as: $t\frac{1}{2} = \ln 2 / \lambda_z$
tlast	Last time point where the concentration is above the limit of quantification
CL	Clearance $CL = \text{dose} / AUC(0-\infty)$
CLss	Steady-state Clearance $CLss = \text{dose} / AUC(0-\tau)$ for multiple dose
Vz	Volume of distribution $Vz = \text{dose} / (\lambda_z \times AUC(0-\infty))$ for single dose; $Vz = \text{dose} / (\lambda_z \times AUC_{\text{tau}})$ for multiple dose
Vdss	Volume of distribution at steady-state $Vdss = CL \times MRT_{IV}$ for single dose Or $Vdss = CLss \times MRT_{IV}$ for multiple dose
AR 0,AUC	$AR_{0,AUC} = AUC(0-\tau)_{\text{week4}} / AUC(0-\tau)_{\text{week1}}$
AR 0,Cmax	$AR_{0,Cmax} = Cmax_{\text{week4}} / Cmax_{\text{week1}}$

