### 3. PLANNED ANALYSES

#### 3.1. Part 1A and 2A: Dose Escalation (Monotherapy and combination therapy with dostarlimab)

Dose escalation for GSK3745417 monotherapy will begin with a starting dose of 0.1 mg in both Arm A1 and Arm A2. There will be two arms in Part 1A: GSK3745417 monotherapy at every 1-week interval (Q1W) in Arm A1, and GSK3745417 monotherapy at every 3-week interval (Q3W) in Arm A2. The first 3 participants in the first 4 dose levels in each arm will begin treatment  $\geq$ 48 hours apart to allow assessment of initial safety data in each participant before beginning the next participant's treatment. This staggered dosing start is not required for participants enrolling at previously cleared dose levels and may be waived once sufficient data are available. In exceptional cases, intra-participant dose escalation allowing participants to move from a lower to a higher dose not exceeding the MTD will be discussed with investigators and approved by the GSK Medical Monitor. Once a 21-day for Arm A1 or 29-day for Arm A2 DLT evaluation period has been completed, BLRM analysis will be performed to guide the dose level to which the next 3 participants will be assigned based on the posterior probability of the DLT rate.

Select outputs will be provided by S&P for monotherapy dose escalation meetings (Part 1A). These are indicated in Appendix 10 by the DEM reporting effort. The following outputs were created for DEMs only and are therefore not referred to in the main RAP text:

- A summary of the number of DLTs, adverse events (AEs) and serious adverse events (SAEs) for all DLT evaluable subjects
- A summary of the number of events and subject by maximum grade for DLT evaluable subjects
- A listing of serious adverse events for DLT evaluable subjects
- A listing of grade  $\geq 3$  laboratory data for complete blood count (CBC) with differential for DLT evaluable subjects

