### 9.2.2. Summary Measures

All derived PK parameters will be listed. The listing will include treatment group, site ID, unique subject ID, subject ID, age, sex, race detail, analysis visit, actual dose (mg) and the PK parameters listed in [Table 3](#).

All derived PK parameters will be summarised descriptively by treatment. For each of these parameters, except Tmax, the following summary statistics will be calculated for each dose

level: median, minimum, maximum, arithmetic mean, 95% CI for the arithmetic mean, StD, between subject coefficient of variation ( $\%CV_b = 100 * (\sqrt{\exp(SD^2)} - 1)$ ) (where  $SD = SD$  of natural log transformed data), geometric mean (the  $n^{\text{th}}$  root of the product of the  $n$  values), 95% CI for the geometric mean and standard deviation of the log- transformed data. For  $T_{\text{max}}$ , median, maximum, minimum, arithmetic mean, 95% CI, and standard deviation will be calculated.

All PK parameters will be reported to at least 3 significant digits, but to no more significant digits than the precision of the original data.

The following pharmacokinetic statistical analyses will only be performed if sufficient data are available (i.e., if participants have well defined serum profiles). A minimum of 3 doses will be required to assess dose proportionality (across all treatment cohorts). Analyses may not be performed on  $C_{\text{max}}$  or  $AUC$  if the team considers there are a large amount of data either below the limit of quantification or non-calculable for at least one of the three doses.

Dose proportionality of GSK3745417 will be assessed by visual inspection of:

[figure not shown]
- Scatter plots (+geometric mean and 95% CI, as appropriate) of GSK3745417 dose-normalized PK parameter vs dose for  $AUC(0-\infty)$  [or if not calculable for the majority of participants, then  $AUC(0-t)$ ] and  $C_{\text{max}}$

The PK parameters will be dose-normalized by the actual dose that each participant received (i.e.  $C_{\text{max}}/\text{actual dose}$ ).

Analysis procedures will follow *Non-Compartmental Analysis of Clinical Pharmacokinetic Data* (VQD-REF-015788 [1.0]) and GSK PK Display Standards unless otherwise noted.

[figure not shown]

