## 12.6.2. Study Population

Treatment Assignment	

 
As defined in Section 0, in the All Treated analysis set participants will be assigned to the cohort of the first dose they received, regardless of any permanent dose reductions or regimen changes. This will be derived from exposure data.
 
If the dose level is reduced or the dose regimen changes during the treatment period from what the participant initially received, study population and safety data will be summarized by the dose level the participant initially received. However, PK data will be summarized by the actual dose received for each visit, see below.
 
The most common dose regimen change (within either Part 1A or Part 2A) is expected to be a reduction in frequency, that is, reduction from Q1W dosing to Q3W dosing.
 
Data on participants who have crossed over from Part 1A to Part 2A will generally be presented separately in crossover cohorts, see Section 6.1.3 for details.
 
	
Treatment Assignment: PK	

 
For PK summaries and analyses, participants are assigned to the cohort of the actual dose received at that visit.
 
CCI
 
	

 
Participants who receive <90% of the planned dose level for a specified visit will have their data excluded from the relevant tables and figures for that visit (as it cannot be assigned to an existing cohort).
 
CCI
 
	

schedule while they are on monotherapy. This is due to a limitation in data collection, as regimen change during the study was not collected on the eCRFs. Due to the short half-life of GSK3745417, this treatment assignment approach should have a negligible impact on the PK analyses.
	
Time since Initial Diagnosis	

 
Calculated as the number of [Days] from the Date of Initial Diagnosis: 
 
First Dose Date = Missing → Elapse Time = Missing
 
Date of Initial Diagnosis = Completely/partially Missing → Elapse Time = Missing
 
Otherwise → Elapse Time = First Dose Date – Date of Initial Diagnosis + 1
 
 
 
	
Start of Subsequent Anti-Cancer Therapy	

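### Accumulation ratios in SAP Table 3 have no dose term or same-dose condition, so a planned change of dose level between Week 1 and Week 4 is read as accumulation or its absence (minor)

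*SAP*

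**What the plan says.** Table 3 (SAP Section 9.2.1) gives two accumulation ratios, "AR_{0,AUC} = AUC(0-\tau)_{\text{week4}} / AUC(0-\tau)_{\text{week1" and "AR_{0,Cmax} = Cmax_{\text{week4}} / Cmax_{\text{week1". Neither contains the dose, and no condition is attached to the doses given at the two visits. Section 9.2.2 has every derived parameter listed and summarised by treatment, so both ratios reach Table 4.2.

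Dose changes within a participant are foreseen in three places:
- Section 12.6.2 opens one of its assignment rules with "If the dose level is reduced or the dose regimen changes during the treatment period from what the participant initially received".
- Section 3.1 allows, exceptionally and with Medical Monitor approval, "intra-participant dose escalation allowing participants to move from a lower to a higher dose not exceeding the MTD".
- The notes for Table 4.2 (Section 12.10.6) provide a footnote for the case where n exceeds N because someone received a dose other than the one first assigned.

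On grouping, Section 12.6.2 states: "For PK summaries and analyses, participants are assigned to the cohort of the actual dose received at that visit". Section 9 says the same. Section 12.6.2 also drops a participant from a visit's tables and figures when less than 90% of the dose planned for that visit was given.

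Dose normalisation appears once, under the dose-proportionality plots in Section 9.2.2: "The PK parameters will be dose-normalized by the actual dose that each participant received". It is not extended to the accumulation ratios.

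**The concern.** An accumulation ratio is meant to show how exposure builds up when the same dose is repeated. If the dose at Week 4 differs from the dose at Week 1, the Table 3 formula mixes accumulation with the dose change. A reduction can hide accumulation and an increase can imitate it.

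The grouping rule does not repair this. It works for a parameter from one visit. A ratio built from two visits would, on the natural reading, be filed as a Week 4 parameter under the Week 4 dose, while its denominator comes from a different dose. In a small cohort, one such ratio can move the summary visibly.

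**Working it through.** The SAP states no value for either ratio, so there is no figure to reproduce. The check is algebra with stated assumptions.

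**1. What the formula returns.** Let X be Cmax or AUC(0-tau), D the actual dose, and 1 and 4 the weeks. Assume exposure is proportional to dose. Then

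X4 / X1 = true ratio × (D4 / D1).

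| D4/D1 | True ratio | Table 3 returns |
|---|---|---|
| 0.5 | 1.0 | 0.50 |
| 0.75 | 1.0 | 0.75 |
| 1.5 | 1.0 | 1.50 |
| 2 | 1.0 | 2.00 |
| 0.5 | 2.0 | 1.00 |

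In the last row a real doubling of exposure is reported as no accumulation.

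**2. How large real accumulation is likely to be.** Section 12.6.2 calls the half-life short but gives no number. Assume mono-exponential decline and half-lives of 1 to 48 h. The steady-state ratio is 1 / (1 − exp(−ln 2 × tau / t½)).
- Weekly (tau = 168 h): 1.000 at 1 h, 1.008 at 24 h, 1.097 at 48 h.
- Three-weekly (tau = 504 h): 1.000 at 1 to 24 h, 1.001 at 48 h.

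Over this range a dose step would outweigh the accumulation being measured.

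**3. What the 90% rule covers.** It compares the dose given with the dose planned for that visit. A Week 4 infusion below 90% of plan therefore leaves the Week 4 tables and figures. A planned move to another level, given in full, passes. Doses between 90% and 100% of plan also pass, and shift the ratio by a factor between 0.90 and 1/0.90 = 1.11. The SAP does not say whether a Week 4 ratio is dropped when the Week 1 infusion was the incomplete one.

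**4. Effect on a cohort summary (illustration).** Under Section 12.6.2 the participant's Week 4 data sit in the Week 4 dose cohort. Let that cohort have three other participants and let every true ratio be 1. The two-fold step is an assumption: the SAP's two-fold limit in Section 3.1.1 applies between cohorts, and no within-participant step size is visible.
- Dose doubled, ratios 1, 1, 1, 2: geometric mean 2^(1/4) = 1.19; arithmetic mean 5/4 = 1.25.
- Dose halved, ratios 1, 1, 1, 0.5: geometric mean 0.5^(1/4) = 0.84; arithmetic mean 3.5/4 = 0.875.

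In general the geometric mean is (D4/D1)^(1/n), with n the number in that cohort. With n = 9 it is 1.08 for a doubling and 0.93 for a halving.

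**5. With the fix.** Restricting the ratio to equal doses sets D4/D1 to 1, so the true ratio is returned. Dividing each term by its own dose does the same under proportionality.

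**The case against.** The case against is substantial on frequency and size.

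- **Dose changes are not presented as common.** Section 12.6.2 expects the most frequent regimen change to be from weekly to three-weekly dosing, which leaves the dose per infusion alone. Escalation within a participant is exceptional. On the three-weekly schedule Week 4 is only the second dosing visit, so there is little time for a change. This stands.
- **The 90% rule is a real safeguard.** A reader might infer that any departure from the assigned dose distorts the summaries. The SAP does not support that: incomplete Week 4 infusions are already removed from that visit's tables and figures. Only planned moves to another level, and small shortfalls, remain.
- **The cohort effect is easily overstated.** A reader might keep a doubled participant with two members of the starting cohort and obtain 2^(1/3) = 1.26. Section 12.6.2 moves that participant's Week 4 data to the new dose cohort, so that example does not follow the SAP.
- **Little depends on the ratios.** The secondary endpoint names AUC(0-tau), Cmax and half-life. Accumulation ratios are additional parameters, derived if the data allow, summarised descriptively, and used in no decision shown.
- **Part of the text cannot be seen.** Some of the PK assignment rule is redacted, and the sponsor's non-compartmental guide is not at hand. A same-dose condition there cannot be ruled out. None is visible, and Table 3 as written gives the wrong quantity for the participants concerned.

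These points limit the consequence. They do not make the formula measure accumulation when the dose has changed.

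**Conclusion.** The point holds, and it is minor. For a participant moved to another dose level between Week 1 and Week 4, the two ratios in Table 3 report accumulation multiplied by the dose ratio. The result would be summarised in the Week 4 dose cohort with a denominator from another dose. The size depends on the dose step, which the SAP does not give, and on approximate dose proportionality, which it assesses only by visual inspection. The cohort figures of about 1.19 and 0.84 are illustrations, not expected results.

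A reader might go further and conclude that the accumulation results are biased in general. The SAP does not support this: participants with the same dose at both visits are unaffected, no count of dose changes is given, and that count is probably small. Nor do the named secondary PK endpoints depend on the ratios.

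**What to change.** In Table 3, add that the accumulation ratios enter the summary only where the actual doses at Week 1 and Week 4 agree within a stated tolerance, for example the 10% already implied by the exclusion rule in Section 12.6.2. State that the ratio belongs to the cohort of that common dose. Put the remaining ratios in the parameter listing with both actual doses. Listing 25 as specified fills in the actual dose only when it differs from the expected dose, so a planned change might not show.

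The cost is one line in Table 3, one listing note, and the loss of a few ratios from the summary. The actual dose at each visit is already needed for PK grouping and for the proportionality plots, so no new data are required.

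Dividing each term by its own actual dose keeps every ratio and could serve as an alternative or a sensitivity display. It assumes approximate dose proportionality, which the same-dose restriction does not.
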